6.2 LONG TERM FOLLOW UP ASSESSMENTS

There are no long term follow up assessments. We will advise participants that the overall findings of the study will be displayed on the study website. The research team will not initiate any other follow up, correspondence or study visits.

6.3 STORAGE AND ANALYSIS OF SAMPLES

Urine samples (up to 50mls) will be collected at every study visit during phase two. These will be analysed for proteinuria (albumin-creatinine level) by NHS Lothian laboratories. Excess sample will be processed and stored in the Edinburgh Reproductive Tissue Biobank within the Queen's Medical Research Institute (QMRI).

The Edinburgh Reproductive Tissue Biobank has standard operating procedures (SOPs) for processing and storage of samples. Biological samples will be retained at the end of the study in QMRI ultra-low temperature freezers, and destroyed after ten years.

7 DATA COLLECTION

A unique study identifier will be allocated to each participating woman at recruitment and this unique number will be used for data collection within the study. Identifiers are stored separately from the main data tables and only delegated members of the team will be granted access to these identifiers.

Data will be collected for all participants as part of *I-TEST* study (within which this sub-study is nested) by a delegated member of the research team using an electronic case report form (eCRF). Data collected included: a) socio-demographics, medical and obstetric history b) details of the current pregnancy including pregnancy complications. c) birth outcomes including birthweight, gestation at birth, baby sex, mode of birth, indication for delivery, admission to the neonatal unit, respiratory distress, Apgar scores and umbilical cord pH.

7.1 Source Data Documentation

Source data is defined as all information in original records and certified copies of original records or clinical findings, observations, or other activities in a clinical study necessary for the reconstruction and evaluation of the study. Source data are contained in source documents.

Source documents are original documents, data and records where source data are recorded for the first time.

The Investigator will maintain source documents for each patient in the study, consisting of mother and baby case and visit notes (hospital or clinic medical records) containing demographic and medical information, laboratory data, and the results of any other tests or assessments. All information relevant to a participant's general medical history on eCRFs must be traceable to these source documents in the patient's case notes.

7.2 Case Report Forms

Electronic case report forms will be utilised.

8 DATA MANAGEMENT

8.1 Personal Data

The following personal data will be collected as part of the research: Demographic, clinical and personal data including CHI-number; postcode; contact telephone number; email address; date of birth.

The Chief Investigator (CI) is the custodian for the study data.

8.2 Data Information Flow

Data will be extracted from the electronic health record of mother and baby and, after anonymisation, clinical details entered into the study database. Each patient will be allocated a study number that will be used to identify the patient, no personal data will be recorded in the database. Data will be filled in at each study visit.

8.3 Data Storage

Personal data will be stored by the research team on a password protected secure NHS computer in a locked office at Royal Infirmary of Edinburgh.

All local paper files containing personal data will be held in filing cabinets in NHS offices that will be locked when unattended. Access to the study documents will be by the study team only.

Research data collected will be stored on secure servers hosted by the University of Edinburgh that require user authentication.

8.4 Data Retention

Personal data will be stored for 5 years.

8.5 Disposal of Data

Research data will be archived after the end of the study, and made available in de-identified format to satisfy data sharing requirements at the end of the study.

8.6 External Transfer of Data

Data collected or generated by the study will be transferred to Swansea University for the purpose of running personalised simulations of the maternal circulations using computational models, on behalf of the Sponsors. Metrics produced from these simulations will be returned to the University of Edinburgh for further analysis by the research team.

Participants will be informed about the need for the study to share anonymised data with Swansea University for analyses.

Participants consent to the use of information about them to support other research in the future, and that the information may be shared anonymously with other researchers, whatever happens to the participant.

Data Transfer will be in accordance with General Data Protection Regulations, International Conference on Harmonisation Tripartite Guideline for Good Clinical Practice (ICH GCP) and SOPs that cascade from the practices defined by the Academic and Clinical Central Office for Research and Development (ACCORD) SOPs.

Delegated research staff will enter the data required by the protocol into the eCRF following training in the definitions and methods used in completing the eCRF.

On completion of data collection, the Investigator must certify that the data entered into the eCRF is complete and accurate.

Data verification and cleaning will be performed as per local procedures and detailed in the Data Management Plan.

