2.2 ENDPOINTS

2.2.1 Primary Endpoint

Generation of circulatory models which simulate blood flows and vascular resistances throughout the maternal circulation at serial timepoints throughout gestation.

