9.2 PROPOSED ANALYSES

Participant height and detailed cardiovascular and Doppler ultrasound data collected at study visits will be used to personalise patient-specific cardiovascular models, using a two-tier parameter estimation algorithm within a closed-loop 1D-0D circulatory model of pregnancy as described in Carson et al(13). We will extract outputs from these models including predicted measures of aortic diameter and elasticity, and retinal and placental vascular bed resistances.

We will apply correlation analysis to phase one data, to assess relationships between ophthalmic artery Doppler indices and model-predicted aortic and retinal vascular metrics. This will establish whether individual Doppler indices reflect upstream or downstream vascular properties. We will also assess correlation between ophthalmic artery and uterine artery Doppler indices which might suggest synergy between retinal and uteroplacental circulations. Descriptive statistics will be used to compare measures of ophthalmic artery blood flow and retinal vascular resistances between cases and controls, identifying possible candidate biomarkers.

In phase two, we will use a linear mixed effects regression approach to assess longitudinal changes in vascular metrics within individuals, and identify differences in metric trajectories for pregnancies affected by placental dysfunction. We will validate candidate biomarkers of vascular and placental dysfunction by testing associations with proteinuria and 36-week PIGF levels (from blood samples collected as part of the *I-TEST* study), using linear models adjusted for common co-variates, adjusting for multiple comparisons. Separate subgroup analysis will be performed for participants on antihypertensive treatment.

We will assess the relationship between estimates of retinal vascular resistances generated from computational modelling and structural parameters derived from retinal vascular imaging in the *I-TEST study*, using data from phases one and two. This will be through analysis of correlation between model-prediction retinal vascular resistance and metrics derived at the same gestation from retinal imaging, for individual participants.

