10 ADVERSE EVENTS

All researchers involved in this study envisage that the extent of adverse events would remain low. All measurements are non-invasive and have been conducted safely in pregnancy without any adverse events. However, in the event of an adverse event, the appropriate investigator will investigate the causality, seriousness and severity. Should any woman be anxious about any of the tests or findings, our experienced team will be available for discussion. The only identified risk is in data security (Table 1).

Table 1: Main risks to data security

Risk description	Security controls	Likelihood	Impact	Risk
Unauthorised access to patient records	NHS Lothian contract of employment. Personnel mandatory training	Low	Medium	Low
Unauthorised access to NHS Lothian servers	Role based and password protected access to NHS Lothian systems with staff working on dedicated NHS Lothian equipment is secure locations	Low	High	Medium
Risk of disclosure of data leaving the NHS Lothian server	Data extracts pseudonymised, disclosure checked before release. SOPs and training according to national guidance	Low	High	Medium
Loss or unauthorised access to data during data transfer between the University of Edinburgh and Swansea University	Data release checked before release. A secure File Transfer Protocol process must be used	Low	Medium	Medium

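### The transfer to the modelling centre is not limited to the model inputs and nothing masks case status or outcome, so masked generation of the outputs later compared by group is not assured

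*Protocol*

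**What the plan says.** Protocol section 8.6 governs what goes to the centre that runs the simulations: "Data collected or generated by the study will be transferred to Swansea University for the purpose of running personalised simulations". The results then come back: "Metrics produced from these simulations will be returned to the University of Edinburgh for further analysis by the research team". On protection, the same section states: "Participants will be informed about the need for the study to share anonymised data with Swansea University for analyses". The data-security table in section 10 adds, for data leaving the health board's server: "Data extracts pseudonymised, disclosure checked before release".

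Section 9.2 describes what the fitting uses: "Participant height and detailed cardiovascular and Doppler ultrasound data collected at study visits will be used to personalise patient-specific cardiovascular models", and how it is done: "using a two-tier parameter estimation algorithm within a closed-loop 1D-0D circulatory model of pregnancy".

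Section 2.2.1 makes the models themselves the primary endpoint: "Generation of circulatory models which simulate blood flows and vascular resistances throughout the maternal circulation". Section 9.2 then uses their outputs by group. For phase one: "Descriptive statistics will be used to compare measures of ophthalmic artery blood flow and retinal vascular resistances between cases and controls". For phase two, a linear mixed model looks for different trajectories in pregnancies with placental dysfunction. Section 2.2.2 lists discrimination of affected from healthy pregnancies as a secondary endpoint.

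**The concern.** A quantity that will be compared between groups is best produced by people who do not know the group. Here the quantity is a set of fitted parameters for each woman, such as retinal and placental bed resistances, produced at a separate centre. If those fitting the models can see who is a case, or how the pregnancy ended, any judgement in the fitting can lean towards the expected pattern. That judgement might concern which reading to use, whether a fit is acceptable, or whether to rerun or discard it.

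A bias of this kind would sit inside the candidate biomarkers before the analysis begins. It would carry into the case-control description, the phase two trajectories and the prediction models. The k-fold cross-validation in section 9.2 would not remove it, because training and test folds would share the same affected predictor.

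The fitting stage is also where a mask is easiest to keep. Fitting and group analysis are already assigned to different institutions, and the fitting does not list group as an input.

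**Working it through.** No figure in the protocol bears on this point, so the check is a reading of the relevant sections side by side.

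1. **Scope of the transfer (8.6) against stated need (9.2).** Section 8.6 speaks of study data and gives a purpose, running the simulations, but no list of fields. Section 9.2 lists height, cardiovascular measurements and Doppler measurements. Case status, diagnosis, treatment, proteinuria, PlGF and birth outcome are not listed as inputs. The transfer wording is therefore wider than the need, although its stated purpose points towards a narrower extract.

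2. **Controls on the transfer (8.6; section 10, Table 1).** Anonymisation, pseudonymisation, a disclosure check and secure transfer all guard identity. A record under a study number can still carry a case flag or a birthweight.

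3. **Masking.** No section of the protocol mentions masking or blinding of the modelling step, or locking the outputs before they are linked to status or outcome.

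4. **Whether status exists when fitting is done.** In phase one it does: section 4.1 recruits 10 women with uncomplicated pregnancies and 10 with diagnosed disease. In phase two, diagnoses and birth outcomes accrue during the study. Section 9.1 also uses data from the first 50 women to calculate effect sizes and inform later data collection, so group findings may be known before later women are fitted.

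5. **Where discretion could enter.** Section 9.2 specifies an estimation algorithm, which limits judgement. Section 6.1 nevertheless leaves several possible inputs: cardiac output by either of two methods; pulse wave velocity repeated three times or until two readings agree within 0.5 m/s; and two ophthalmic waveforms per eye. The protocol does not say which of these values enter the fit, or what happens when a fit fails.

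6. **Size.** An estimate would need the number of fits per woman, the proportion rerun or rejected, and the shift that each such decision causes. The protocol gives none of these. Phase one women are seen fortnightly until birth, so even the number of fits per group is not fixed. No estimate of bias can be derived.

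**The case against.** The strongest objection is that the protocol is silent rather than wrong. A reader might infer that all study data go to the modelling centre and that the outputs are produced unmasked. The text supports neither. The transfer is tied to running simulations, section 9.2 names a narrow set of inputs, and nowhere is status or outcome said to be sent. Some of the sensitive items, namely birth outcomes (section 7) and PlGF (sections 2.1.2 and 9.2), are collected through the parent study and may not fall within this study's transfer at all. This objection stands, and it is why the point is put as a lack of assurance.

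Second, fitting is algorithmic and follows a published method. No section describes manual tuning or dropped fits at the modelling centre, and some repeat-reading rules are set at the bedside. This also stands: the risk is confined to whatever discretionary steps exist.

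Third, the group comparison is assigned to the Edinburgh team, discrimination is a secondary endpoint, and phase one is exploratory and descriptive. That lowers the stakes. It does not answer the point, because a bias introduced when the metrics are made would arrive with them.

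Fourth, extract fields and refit rules may sit in an analysis plan or in the Data Management Plan that section 8.6 mentions, neither of which is shown. That is fair for the details. The scope of the transfer, however, is set in section 8.6, and a mask must be in place before the data leave.

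Last, masking would be incomplete. Blood pressure and Doppler values can betray disease, and so can the extra fortnightly visits offered in phase two to women with a diagnosis.

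**Conclusion.** The point holds in a limited form. Section 8.6 does not confine the transfer to the section 9.2 inputs, and nothing in the protocol keeps case status, diagnosis or outcome from those fitting the models. Masked generation of outputs that are later compared by group is therefore not assured in either phase.

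It would go too far to say that the modellers are unmasked or that the outputs are biased, because the protocol states neither. The conclusion assumes only that some fitting decisions are open to judgement; if there were none, knowledge of status could not alter a fit. The size of any bias cannot be estimated from the documents. This is an inexpensive safeguard worth adding, not an error in a stated figure.

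**What to change.** In section 8.6:

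- Restrict the extract to the section 9.2 inputs (height, cardiovascular and Doppler data) plus gestation at the visit, under study number. Gestation is not listed in section 9.2 and is added on the assumption that a model of pregnancy at serial timepoints needs it.
- Withhold group, diagnosis, treatment, biomarkers and outcomes until the outputs for that phase, or for the look at the first 50 women, have been returned and locked.
- Apply the same written refit and rejection rule to every woman, and report failed or rerun fits by group once status is linked.

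The cost is a small data-handling step and a few sentences of text. A smaller extract also reduces the disclosure risk listed in section 10. The protocol should acknowledge that the mask is partial, for the reasons given above.

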8.7 Data Controller

A data controller is an organisation that determines the purposes for which, and the manner in which, any personal data are processed.

The University of Edinburgh and NHS Lothian are joint data controllers along with any other entities involved in delivering the study that may be a data controller in accordance with applicable laws (e.g. the site).

8.8 Data Breaches

Any data breaches will be reported to the University of Edinburgh ([contact]) and NHS Lothian ([contact]) Data Protection Officers who will onward report to the relevant authority according to the appropriate timelines if required.

9 STATISTICS AND DATA ANALYSIS

9.1 SAMPLE SIZE CALCULATION

The emphasis of phase one is integration of measured parameters into computational models of the maternal circulation. There are no comparative pregnancy cohorts, studied using haemodynamic modelling in this way, on which to base a power calculation. Given the detailed data collected at multiple time points, and additional insights afforded by a modelling approach, a sample of 10 women with uncomplicated pregnancies and 10 with disordered pregnancies will provide proof-of-principle data and indicate potential candidate biomarkers.

Regarding phases two, there are no existing pregnancy cohorts of similar phenotypic depth studied with repeated measures. Therefore, we do not have access to estimates of effect sizes to support a formal sample size calculation. After recruitment of the first 50 women, we will use initial data to calculate effect sizes and inform data collection for further recruited participants. We propose repeated longitudinal assessment of a cohort of 100 women, and aim to recruit 115 women to allow for pregnancy losses and losses to follow up.

9.2 PROPOSED ANALYSES

Participant height and detailed cardiovascular and Doppler ultrasound data collected at study visits will be used to personalise patient-specific cardiovascular models, using a two-tier parameter estimation algorithm within a closed-loop 1D-0D circulatory model of pregnancy as described in Carson et al(13). We will extract outputs from these models including predicted measures of aortic diameter and elasticity, and retinal and placental vascular bed resistances.

We will apply correlation analysis to phase one data, to assess relationships between ophthalmic artery Doppler indices and model-predicted aortic and retinal vascular metrics. This will establish whether individual Doppler indices reflect upstream or downstream vascular properties. We will also assess correlation between ophthalmic artery and uterine artery Doppler indices which might suggest synergy between retinal and uteroplacental circulations. Descriptive statistics will be used to compare measures of ophthalmic artery blood flow and retinal vascular resistances between cases and controls, identifying possible candidate biomarkers.

In phase two, we will use a linear mixed effects regression approach to assess longitudinal changes in vascular metrics within individuals, and identify differences in metric trajectories for pregnancies affected by placental dysfunction. We will validate candidate biomarkers of vascular and placental dysfunction by testing associations with proteinuria and 36-week PIGF levels (from blood samples collected as part of the *I-TEST* study), using linear models adjusted for common co-variates, adjusting for multiple comparisons. Separate subgroup analysis will be performed for participants on antihypertensive treatment.

We will assess the relationship between estimates of retinal vascular resistances generated from computational modelling and structural parameters derived from retinal vascular imaging in the *I-TEST study*, using data from phases one and two. This will be through analysis of correlation between model-prediction retinal vascular resistance and metrics derived at the same gestation from retinal imaging, for individual participants.

In predictive outcome modelling, we will adhere to PROBAST and TRIPOD guidelines(16,17). For continuous outcomes, such as birthweight, this will be approached as a multivariate linear regression task. For categorical outcomes, including occurrence of specified pregnancy complications, we will apply a logistic regression approach only for sufficiently balanced data. Training/test data splits will be performed using k-fold cross validation. We will evaluate classifiers in terms of precision, recall and area under the receiver-operator curve, and compare these with baselines based on demographic and routine clinical evaluation data.

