4 STUDY POPULATION

4.1 NUMBER OF PARTICIPANTS

Phase one: 20 pregnant women with singleton pregnancy recruited after 34 weeks' gestation, including 10 with uncomplicated pregnancies and 10 with diagnosed pre-eclampsia (as per International Society for the Study of Hypertension in Pregnancy guidelines) or fetal growth restriction (as per Delphi criteria for small for gestational age)(14,15).

Phase two: 100 women with singleton pregnancy, recruited after antenatal booking and prior to 15 weeks' gestation.

This will be a single site study, involving only participants with pregnancies booked within NHS Lothian.

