6 STUDY ASSESSMENTS

6.1 STUDY ASSESSMENTS

All study visits will take place at the Royal Infirmary of Edinburgh. Where possible, visits will be undertaken to coincide with a routine clinical visit, or with a *I-TEST* study visit for retinal imaging.

The following datasets will be collected at study visits (in addition to data gathered through the *I-TEST* study). In phase one, these will be at fortnightly intervals (±5 days), starting after 34 weeks gestation and continuing until birth. In phase two, these will be at 12, 28 and 36 weeks' gestation and 6 weeks postnatally (±3 weeks for each timepoint), with additional (up to fortnightly) study visits offered for women with diagnosed pre-eclampsia or fetal growth restriction, if these can be aligned with scheduled clinical appointments.

Maternal physiological data:

· Maternal height and weight will be measured.

Maternal cardiovascular data:

- Heart rate and systolic and diastolic blood pressure will be measured lying, sitting and standing.
- Echocardiography or electrocardiography (ECG) cardio-impedance will be conducted for measurement of cardiac output ± aortic size.
- Pulse wave velocity: aortic central pulse wave velocity will be assessed with a tonometry-based device placed sequentially over the carotid and femoral artery in conjunction with simultaneous ECG recording. Peripheral pulse wave velocity will then be assessed with a tonometry-based device placed sequentially over either the carotid and radial arteries, or femoral and popliteal/tibial arteries, in conjunction with simultaneous ECG recording. The distance between points of pulse wave detection will be measured manually to allow calculation of central and peripheral pulse wave velocities. The measurement of pulse wave velocities, both centrally and peripherally, will be repeated three times, or until at least two measures are within 0.5m/s.

Ultrasound assessment:

- Maternal uterine artery Doppler measurements will be made and the pulsatility index from both uterine arteries will be recorded (this assessment is already carried out on all *I-TEST* participants at the 36 week visit *I-TEST-M* would involve further repeated measurements at all study visits).

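### Phase one names only correlation for repeat visits in a mixed case-control sample; clustering and case mix should be handled, and the claim to establish a mechanism softened

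*Protocol*

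**What the plan says.** The phase one sample is a deliberate mixture (Protocol 4.1): "20 pregnant women with singleton pregnancy recruited after 34 weeks' gestation, including 10 with uncomplicated pregnancies and 10 with diagnosed pre-eclampsia" or fetal growth restriction. Each woman is measured repeatedly (6.1): "In phase one, these will be at fortnightly intervals (±5 days), starting after 34 weeks gestation and continuing until birth". Section 9.1 offers no power calculation and relies partly on those repeats to justify the number: "Given the detailed data collected at multiple time points, and additional insights afforded by a modelling approach, a sample of 10 women" in each group is expected to give proof of principle.

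Section 9.2 assigns methods by phase. For phase one: "We will apply correlation analysis to phase one data, to assess relationships between ophthalmic artery Doppler indices" and the aortic and retinal outputs of the circulatory model. The inference follows directly: "This will establish whether individual Doppler indices reflect upstream or downstream vascular properties". A second correlation is added: "We will also assess correlation between ophthalmic artery and uterine artery Doppler indices which might suggest synergy between retinal and uteroplacental circulations". For the group contrast: "Descriptive statistics will be used to compare measures of ophthalmic artery blood flow and retinal vascular resistances between cases and controls".

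The next paragraph of 9.2 gives phase two a linear mixed effects model, and gives its biomarker validation covariate and multiplicity adjustment. For phase one the section does not name the unit of analysis or say how repeats, case status or gestation enter. A later paragraph matches gestation within participant, but only for the correlation of modelled retinal resistance with retinal imaging.

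**The concern.** The two phases share a data structure, namely several visits per woman, but only phase two has a method that fits it. Two separate difficulties follow for the phase one correlations.

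- **Clustering.** Visits from one woman resemble each other. Counting each as an independent pair makes intervals too narrow and p-values too small.
- **Case mix.** Half the sample is chosen for disease. Any two metrics that both shift with disease will correlate across the whole sample, even if they are unrelated among cases and unrelated among controls. Averaging to one value per woman does not remove this.

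At stake is the reading of two results: whether a Doppler index reflects aortic or retinal properties, and whether the retinal and uteroplacental circulations move together. The study expects both ophthalmic and uteroplacental measures to relate to placental dysfunction (1.1 and 1.2). Some ophthalmic-uterine correlation is therefore to be expected from the sampling alone.

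**Working it through.** **No figure to reproduce.** The protocol gives no alpha, effect size, SD, ICC or correlation for phase one.

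**Inputs from the protocol:** 10 cases and 10 controls (4.1); fortnightly visits after 34 weeks until birth (6.1).

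**Assumed, with ranges:** 1 to 4 visits per woman; ICC (the share of a metric's variance that lies between women) 0.3 to 0.9, the same for both metrics; case-control shift d of 0 to 1.5 within-group SD in both metrics; nominal two-sided 5% test. Simulations used 8,000 runs per setting and two metrics with no association within either group. The Monte Carlo standard error near 14.5% is √(0.145 × 0.855 / 8000) = 0.4 percentage points.

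**1. Clustering alone (d = 0), all visits pooled as independent**

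| Visits per case / control | ICC 0.3 | ICC 0.5 | ICC 0.7 | ICC 0.9 |
|---|---|---|---|---|
| 1 / 2 | – | 6.8% | 9.0% | – |
| 2 / 3 | 7.0% | 9.2% | 14.5% | 20.7% |
| 3 / 4 | – | 12.2% | 19.6% | – |

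Cross-check by the design effect for a correlation, 1 + (m − 1) × ICC₁ × ICC₂. With m = 3 and both ICCs 0.7 this is 1 + 2 × 0.49 = 1.98. So 60 visits carry the information of 60 / 1.98 ≈ 30 independent pairs, and the approximate rejection rate is 2 × [1 − Φ(1.96 / √1.98)] = 16.4%. That lies between the simulated 14.5% (2 / 3 visits) and 19.6% (3 / 4 visits), as it should.

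**2. Case mix alone, one value per woman**

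In an equal mixture with within-group variance 1, a shift d adds d²/4 to each variance and to the covariance, so r = (d²/4) / (1 + d²/4).

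- d = 0.8: 0.16 / 1.16 = 0.14; rejection rate 8.8%
- d = 1.0: 0.25 / 1.25 = 0.20; rejection rate 13.0%
- d = 1.5: 0.5625 / 1.5625 = 0.36; rejection rate 37.1%

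These are false positives only if the question concerns association within groups.

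**3. Both together (ICC 0.7, 2 / 3 visits)**

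| d | Visits pooled | One mean per woman | One mean per woman, centred within group |
|---|---|---|---|
| 0.5 | 15.9% | 5.9% | 4.8% |
| 0.8 | 24.6% | 10.8% | 5.2% |
| 1.0 | 35.6% | 16.8% | 4.8% |
| 1.5 | 71.1% | 48.0% | 5.1% |

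Over all settings tried, one mean per woman centred within group gave 4.7% to 5.6%.

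**4. Gestation.** A trend shared by both metrics of 0.2 or 0.4 SD per visit moved the pooled rate from 14.5% to 14.3% and 16.2% (ICC 0.7, d = 0). This is a small effect beside the other two.

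**The case against.** **The text is silent, not wrong.** A reader might infer that the protocol ignores clustering. It does not say so. It never states that visits are treated as independent, and repeated-measures correlation is itself a form of correlation analysis. An analysis plan that is not shown may settle this. That much stands. What remains is that the protocol itself picks methods phase by phase, leans on the repeats to justify 20 women, and fixes a strong inference in advance.

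**The case-control comparison.** A reader might carry the rejection rates above over to it. They do not apply, because that comparison is descriptive, has no planned test and so has no type I error. It is also the step to which 9.2 attaches the search for candidate biomarkers. The correlations are not that step.

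**Gestational imbalance.** A reader might infer that cases deliver sooner and so supply fewer and earlier visits. The documents give no birth or entry dates by group. Cases may enter at any time after 34 weeks, and 1.1 says that most pre-eclampsia occurs after 37 weeks, so the imbalance could run either way.

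**The pooled association may be wanted.** If disease-driven variation in resistance is the signal, a correlation across the whole sample is real, and adjusting for case status could remove it. This stands, and it is why the adjusted estimate belongs beside the pooled one and should not replace it.

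**Phase one is exploratory.** Section 9.1 calls it proof of principle, 9.2 words the synergy reading cautiously, and candidates are tested again in phase two. This limits the damage. It does not fit with a claim that correlations in 20 women will establish a mechanism.

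**Conclusion.** The concern holds in a limited form. Section 9.2 names only correlation for phase one data that are clustered by woman and mixed by design, and it attaches a conclusion that this method cannot carry. Pooling visits as independent would raise a nominal 5% error to roughly 7% to 21% with 2 visits per case and 3 per control, depending on an ICC that the documents do not give. With few visits or a low ICC the inflation is slight. Combining the groups induces r of 0.20 to 0.36 for assumed shifts of 1 to 1.5 SD, however the visits are handled. A pooled ophthalmic-uterine correlation therefore cannot by itself suggest synergy between the two circulations. The point concerns the correlations. It is a worthwhile, nearly free improvement to an exploratory step, and it does not threaten the study's validity.

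**What to change.** In section 9.2, for phase one:

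1. Analyse associations with a random intercept per woman, or with repeated-measures correlation plus an analysis of one summary value per woman. Report within-woman and between-woman associations separately.
2. Report each association adjusted for case status alongside the pooled estimate, and say which question each one answers.
3. Include actual gestational age at the visit as a covariate, and take it into account when describing case-control differences.
4. Handle repeats in the same way in the retinal imaging correlation that uses both phases, wherever a woman supplies more than one matched point. Some may supply only one, since 1.1 gives I-TEST cohort 2 imaging at 36 weeks only.
5. Replace establish with explore in the sentence on what the Doppler indices reflect.

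The change is to wording and analysis only, with no extra visits or participants, and it uses a method already planned for phase two. The cost is a little more analysis and wider intervals: at 3 visits and ICC 0.7, standard errors grow by about √1.98 ≈ 1.4 relative to pooling. With 20 women, some adjusted estimates will be imprecise and should be reported as such.
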